1.0 Objectives

Our primary hypothesis is that proliferation and expression of other estrogen response genes in hyperplastic breast tissue obtained by RPFNA from high risk women on chronic HRT will be favorably modulated by six months of letrozole relative to placebo without substantially increasing hot flashes or worsening overall quality of life.

To test our hypothesis, we have formulated the following objectives:

- 1.1 To determine whether Ki-67 in hyperplastic foci of breast epithelium obtained by random periareolar fine needle aspiration from postmenopausal high-risk women on HRT is reduced by six months of letrozole.
- 1.2 To determine if letrozole causes an increase in hot flashes, fatigue, pain, stiffness; a deterioration in overall quality of life; as well as deleterious changes in bone turnover markers, total cholesterol:HDL ratio, and C-reactive protein.
- 1.3 To determine if morphologic characteristics as assessed by nuclear morphometric measurements and semiquantitative Masood index score improve with six months of letrozole.
- 1.4 To determine if six months of letrozole in women on a stable dose of hormone replacement results in consistent down modulation of estrogen responsive genes, particularly pS2 and GREB-1.

At the conclusion of this proof of principle study, we will have established a firm clinical and biological basis for a large randomized study of letrozole versus placebo in high-risk postmenopausal women requiring hormone replacement for symptom control with development of breast cancer as an endpoint. If aromatase inhibitor treatment is found to reduce risk of breast cancer in women receiving hormone replacement, it would provide middle age women with tools to alleviate perimenopausal symptoms while minimizing breast cancer risk.

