There were no significant changes in cytomorphology, serum estradiol (Figure 4), testosterone, progesterone, SHBG, ER intensity score, or mammographic density although small reductions were seen for Masood score, estradiol, testosterone, and progesterone (see Table 1). There was no change observed in IGF-1. Results for IGF-1 and ER are similar to those reported by Harper-Wynne et al. [Harper-Wynne 2002] for high risk postmenopausal women not taking hormones.

Figure 4: Estradiol Change with Six Months of Letrozole

[figure not shown]
Reported side effects included hot flashes, arthralgias, fatigue and temporary hair thinning. Median change in hot flash score was 0 (-8 to +9). Seventeen percent reported an increase, 14% a decrease, and 69% reported no change in hot flashes over the duration of the study. Thirty-eight percent reported arthralgias and 41% fatigue when questioned on a monthly basis. The regimen was well-tolerated and only one subject discontinued study prematurely (after 4 months). This is in comparison to the ongoing National Cancer Institute of Canada MAP.2 trial of exemestane vs placebo, where 5 of our accrued 32 subjects discontinued study within the first few months primarily due to hot flashes and related symptoms.

We performed a sub-analysis utilizing the 33 subjects whose baseline Ki-67 was $\geq 2\%$ and who were taking estrogen with or without a progestin, i.e., those who meet the eligibility criteria for the proposed Phase II trial. The baseline, post-study, and change values (Table 2) were similar to those of the entire group of 42 subjects.

Variable/Biomarker	Median Values		
	Baseline	Post-Study	Change (relative)
Age, years	49		
5-Year Gail Risk, %	1.9		
Cytomorphology, Masood Score	14	14	-1
Ki-67, %	5.0	1.6	-3.0 (-0.83)
ER, %	41.0	50.0	-7.0 (-0.11)
ER, IS	0.70	0.53	-0.04 (-0.12)
Mammographic Density, % area	32.8	32.6	0.9
Estradiol, pg/ml	59.9	46.7	-7.4
Testosterone, ng/ml	0.60	0.57	-0.07
Progesterone, ng/ml	3.5	2.5	-0.3
SHBG, nM	57.1	51.5	0.3
IGF-1, ng/ml	185	187	6.6
IGFBP-3, ng/ml	4291	4409	81
IGF-1:IGFBP-3 molar ratio	0.16	0.16	0.005

[figure not shown]
Median baseline Ki-67 was 5.0% and median six month Ki-67 was 1.6%. The median absolute change was a reduction of 3.0% (95% CI, -5.6% to -1.7%). The relative change was an 83% reduction (95% CI, -75% to -10%). A decrease in Ki-67 was exhibited by 28 of the 33 subjects (Figure 5). Median change in Masood cytormorphology index was -1 (range -5 to +1).

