7.0 CLINICAL EVALUATIONS AND PROCEDURES

7.1 Schedule of Events

Study Procedure	Eligibility Period	Treatment Period					4 week follow-up phone contact
	Visit 1 Baseline	Visit 2 On-Study	Monthly Phone Contacts	Visit 3 6 month Visit	Monthly Phone Contacts	Visit 4 12 month visit (optional participation)	
Eligibility Checklist	X						
Informed Consent*	X	X		X		X	
Medical History	X ^o	X ^o					
Breast Exam	X ^o	X ^o		X		X	
Physical Exam	X ^o	X ^o		X		X	
Mammogram	X			X		X	
Ht/Wt/Vital Signs	X	X		X		X	
RPFNA	X			X		X	
CBC, Chemistry, 25-OH vitamin D +	X	X		X		X	
#Fasting blood for: Bioavailable estradiol, testosterone, SHBG, osteocalcin, N-telopeptide, CRP, lipid panel	X			X		X	
#Trough blood (serum) sample				X		X	
Hot flash assessment	X	X	X	X	X	X	X
Fatigue inventory, BCPT Symptom Check List, HAQ Fibromyalgia Impact Questionnaire		X		X		X	
Adverse Events		X	X	X	X	X	X
Dispense Study Agent/Evaluate Compliance		X		X		X	
Concomitant Medication	X	X	X	X	X	X	X
Return Study Agent				X		X	
Off-Study DEXA scan				X	or	X	
Off-Study evaluation							X

*Subjects will sign a consent each time an RPFNA procedure is performed (at KUMC HSC#4601). Only subjects qualifying for the drug/placebo dispensation will sign the study consent document. For sites other than KUMC, they may determine to use the study consent for the screening RPFNA per the site IRB requirements. Subjects will not be officially "on study" until eligibility is determined.

#After a 10-12 hour fast, four gel-clot 7 ml tubes drawn, allowed to clot at room temperature for 30 minutes, spun at 3500 rpm for 15 minutes, and aliquots of serum into 8 polypropylene storage tubes. Tubes to be labeled with subject initials, randomization number and date of draw. Tubes frozen at -80°C and then shipped to KUMC on \geq 5 lbs of dry ice, with pre/post specimens shipped together. Notify KUMC by fax and email prior to shipment.

+CBC, Chemistry, and 25-OH vitamin D to be performed by local laboratory at the expense of site PI (to be included in budget/subject costs)

° Study medical history, breast and physical exams may be done at any point within 3 months prior to randomization and starting study agent. If done prior to Visit 2, any new conditions or changes will be evaluated and documented before randomization and starting study agent.

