7.4 Evaluations During Study Intervention

Monthly Telephone Assessment

Subjects will be contacted by the study coordinator on a monthly basis to review dosing and adverse events. Subjects who are difficult to reach or do not respond to messages and other means of contact may be considered non-compliant. These will be recorded in the source documents and subsequently entered onto CRFs.

7.5 Evaluation at Completion of Randomized Portion of Study at 6 Months (See section 7.1 for Study Calendar)

If necessary for synchronizing scheduling of RPFNA with continued use of letrozole, study agent may be continued for up to one additional month, until the RPFNA is performed. If this occurs, then studies associated with the repeat RPFNA and completion of study will be conducted at that time, not at a calendar six months.

Subjects should NOT take the study drug the day of the procedure and should have blood drawn after a 10-12 hour fast.

Subjects will have a mammogram, RPFNA, CBC/Chem and fasting study bloodwork collected, and a brief physical (including clinical breast exam) performed by a study-associated clinician (see the study calendar, section 7.1 for a comprehensive list). All abnormal findings will be recorded on the physical source document, including duration and severity. Vital signs, height, and weight will be recorded. Percent body fat will also be and percent body fat will also be recorded.

Bloodwork for CBC/Chem (sent to local CLIA lab), fasting (10-12 hour fast) bloodwork and drug trough serum sample will be collected.

Subjects wishing to participate an additional six months in the open label portion of the study will be given an additional 7 month supply and then asked to return for a repeat RPFNA, breast density and other biomarker assays (see study calendar section 7.1).

When the subject has completed taking study agent, any remaining supply will be counted by the study coordinator and recorded, and returned to the Investigational Pharmacy. The assessment of compliance will be performed on the data entered onto the CRF from the pill counts.

When the subject has completed taking study agent, she will receive a DEXA scan to document any effects on bone health.

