10.7 Quality of Life Evaluations

The most frequent adverse events in our pilot trial were arthralgias, fatigue and hot flashes. Consequently, in addition to utilizing the Breast Cancer Prevention Trial (BCPT) symptom scale (used as part of NSABP prevention trials) [Ganz 1995; Day 1999], we will use specific tools geared to the most prevalent symptoms in the pilot study.

The BCPT symptom checklist is a 42 item list of problems common to peri and postmenopausal women and those undergoing anti-hormonal

treatment in prevention trials. Women are asked if they have had the symptom in the past four weeks. If they answer yes, they are asked to grade the severity (0-4). This tool can be used to compute a total score or individual or related items of interest (e.g., three items relate to joint stiffness and arthralgias) may be scored [Stanton 2005].

The Mayo Clinic Hot Flash scoring system was developed by Loprinzi et al. Subjects are asked about their daily number of hot flashes and rate usual severity from 1 to 4. The frequency is multiplied by usual severity to obtain a total score [Loprinzi 2002].

We do not expect an increase in symptoms or hot flash scores for women randomized to letrozole.

The Fibromyalgia Impact Questionnaire (HAQ) is a validated tool routinely used by rheumatologists to evaluate pain, stiffness, and physical functioning. Individual domains or a total score can be utilized in assessment [Wolfe 2004].

The brief fatigue inventory asks the woman to rate her current as well as worst and usual fatigue in the past 24 hours. It also asks her to rate how the fatigue has affected mood, general activity, walking, work relations, and enjoyment of life [Mendoza 1999].

We do not expect an increase in joint pain, stiffness or fatigue for women randomized to letrozole, unless a woman has suboptimal levels of 25-OH vitamin D.

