Evaluation of drug-induced hormonal changes - We will examine whether Letrozole has any effects on serum levels of bioavailable estradiol, and testosterone, determined at baseline and after six months of study medication. We will determine whether addition of letrozole alters the frequency of menopausal symptoms.

Adverse Events and Quality of Life – Change from baseline to six months for hot flash score (Mayo Clinic), fatigue (brief fatigue inventory), overall quality of life (BCPCT), bone turnover markers, HDL/total cholesterol, and C-reactive protein will be compared between the two groups using the two-sample t-test. Similarly, demographic variables (e.g., age, education) and hormonal levels will be tested for use as covariates on each of these endpoints. We will also assess the effects of change in serum hormones (if any) and baseline 25-OH vitamin D levels on incidence and severity of arthralgias and fatigue.

Within Letrozole Comparisons at baseline, 6 and 12 months - On all of our quantitative continuous measures we will perform a repeated measures analysis comparing the 6 and 12 month values to baseline and also with each other. This will give us some preliminary indication whether there is any benefit or detriment of 12 months of treatment. For all the above analyses of exploratory endpoints, as well as for changes in proliferation, results from the 12-month timepoint (following six months of open-label treatment with active agent) will also be analyzed and compared to the baseline and six month values with caution since the double-blind, randomized nature of the comparison is no longer present. However, since

every effort is made to conduct the assessment and quantification of biomarkers without knowledge of treatment arm, the results could be informative.

Since this is a phase IIB trial, the power and sample size for the primary endpoint was determined with a two-sided type I error rate of 5%. All subsequent secondary, tertiary and exploratory analyses will also be tested with a two-sided type I error rate of 5%. This may result in an elevated false positive rate for these secondary and tertiary analyses, however, since this is a Phase IIB study, we felt to control the type I error rate for the secondary, tertiary and exploratory analyses would be too conservative.

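### Hot flash assessments are scheduled monthly, but the only specified between-arm test of the hot flash score uses month 6 alone, so rises that resolve earlier, and the monthly scores of women who stop early, do not enter it

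*Combined protocol and SAP*

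**What the plan says.** The primary hypothesis in section 1.0 is that letrozole modulates the tissue markers favourably "without substantially increasing hot flashes or worsening overall quality of life". Objective 1.2 repeats the question: "To determine if letrozole causes an increase in hot flashes, fatigue, pain, stiffness".

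The Schedule of Events in 7.1 has a row headed "Hot flash assessment". It is marked at Visits 1 and 2, at both blocks of monthly phone contacts, at months 6 and 12, and at the follow-up call. It is separate from the adverse event row, and the other symptom questionnaires are marked at visits only. The instrument in 10.7 is the Mayo score: "The frequency is multiplied by usual severity to obtain a total score". Section 7.4 describes the calls without naming the score: "Subjects will be contacted by the study coordinator on a monthly basis to review dosing and adverse events".

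In 12.2 the between-arm comparison opens "Change from baseline to six months for hot flash score (Mayo Clinic), fatigue (brief fatigue inventory), overall quality of life (BCPCT", continues with laboratory markers, and uses a two-sample t-test. The repeated-measures analysis in 12.2 is within letrozole, at baseline, 6 and 12 months. One further sentence gives no time point or method: "We will determine whether addition of letrozole alters the frequency of menopausal symptoms".

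For women who stop, 12.2 calls all analyses intent-to-treat. It compares grade 3 toxicity or premature discontinuation by Fisher's exact test, and it imputes if more than 5% of data are missing. Section 5.1 asks early stoppers back for biomarkers and does not mention symptom scores.

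**The concern.** A single comparison at month 6 answers whether hot flashes differ at month 6. It does not answer whether letrozole raised them during the six months. If a rise comes early and settles, both arms look alike at month 6. If a woman stops, the scores she gave on the monthly calls are not used in the test.

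The other planned analyses do not replace it. The Fisher comparison pools discontinuation for any cause with grade 3 toxicity, so it does not measure hot flash burden. Moderate hot flashes have no other between-arm comparison with a stated method. Section 10.7 says no increase in hot flash scores is expected on letrozole, and a test that cannot see transient rises errs towards that expectation.

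**Working it through.** **The plan's own figure.** The only sample size is for Ki-67: difference 3.7, SD 5.5, two-sided 5%, 90% power. The normal approximation gives 2 × (1.960 + 1.282)² × (5.5/3.7)² = 46.4, so 47 per arm. The exact t calculation gives 48 per arm, or 96, with power 0.901 at 0.67 SD. Then 96/0.90 = 106.7, so 107, or 108 as an even number. The plan's figures reproduce. None is given for hot flashes, nor an SD or correlation for the score, so what follows is illustration.

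**Precision.** Assume six post-baseline scores with equal variance (set to 1) and equal correlation r between all visits.
- Variance of change at month 6: 2(1 − r).
- Variance of the months 1 to 6 mean minus baseline: 1 + (1 + 5r)/6 − 2r = 7(1 − r)/6.
- Ratio: 7/12 = 0.583 for any r.

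With adjustment for baseline instead of change scores, the ratio is [(1 + 5r)/6 − r²]/(1 − r²) = (1 + 6r)/[6(1 + r)], which is 0.36, 0.44 and 0.51 for r = 0.3, 0.5 and 0.7.

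**Power.** Assume 48 per arm, two-sided 5%, r from 0.3 to 0.7, change scores, and a rise of 0.5 to 0.67 SD of a single score. Example with r = 0.5 and a rise of 0.5: the SD of month-6 change is 1, and the SD for the six-month mean is √(7/12) = 0.764. A sustained rise gives standardized effects of 0.5 (power 0.68) at month 6 and 0.5/0.764 = 0.655 (0.89) for the mean. A rise in months 1 to 3 only gives 0 (0.05) and 0.25/0.764 = 0.327 (0.36). Over the whole range:

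| Pattern of rise | Month 6 alone | Mean of months 1 to 6 |
|---|---|---|
| Months 1 to 3 only | 5% | 27% to 78% |
| Sustained | 54% to 99% | 77% to over 99% |

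**Women who stop.** Section 2.8 gives two rates: 1/42 = 2.4% in the letrozole pilot, and 5/32 = 15.6% of the centre's subjects in a different trial. If stoppers had a 6-point rise (assumed; pilot changes ran from −8 to +9) and nobody else changed, the arm mean counting that rise in full exceeds the completers' mean by:
- 1/42 × 6 = 0.14 points;
- 5/32 × 6 = 0.94 points, an upper bound.

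The upper figure needs the rise to count in all six months. If stoppers leave after month 2 and give no later scores, a baseline-adjusted mixed model under equal correlation carries forward 2r/(1 + 2r) of their excess. The average is then 0.94 × [2 + 4 × 2r/(1 + 2r)]/6 = 0.55, 0.63 and 0.68 for r = 0.3, 0.5 and 0.7.

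**What the other rules catch.** The imputation trigger is 0.05 × 108 = 5.4 women. The pilot rate implies 108/42 = 2.6, so no imputation. The planned 10% dropout implies 10.8, so imputation. At 5/32 on letrozole alone, about 8 of 54 would stop; 8/108 = 7.4%, again above the trigger. With 54 per arm, Fisher's exact test of discontinuation has about 56% power for 15.6% against 2.4%, and about 20% for 10% against 2.4%.

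**The case against.** A reader might infer that women who stop because of hot flashes vanish from the tolerability evaluation. The documents do not support that. Section 12.2 makes premature discontinuation a critical event in a planned between-arm test, calls the analyses intent-to-treat, and imputes above 5% missing. What remains is narrower: no planned use of these women's monthly scores is stated, and nothing says the imputation would draw on them.

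A reader might also take this sentence in 2.8 as the expected rate here: "5 of our accrued 32 subjects discontinued study within the first few months primarily due to hot flashes and related symptoms". It comes from an exemestane-versus-placebo trial, with no arm given for the five women. Section 2.1 says aromatase inhibitor trials exclude users of hormone replacement. The protocol cites it as a contrast with its own pilot, where one of 42 stopped, median hot flash change was 0, 17% reported an increase, 14% a decrease and 69% no change. That objection stands, so 0.94 points cannot be presented as the likely bias.

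Six months also matches the treatment period in the hypothesis, and no passage shows a transient rise on letrozole with hormone replacement. This supports keeping the month-6 contrast. It does not support leaving the scheduled monthly assessments without a between-arm analysis.

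Finally, monthly Mayo scoring is inferred from 7.1, because 7.4 names only dosing and adverse events. This too stands, and the plan needs to settle it.

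**Conclusion.** The point holds in limited form. The specified between-arm test of the hot flash score uses one post-baseline time point although assessments are scheduled monthly, and it cannot detect a rise that has resolved by month 6. Under equal variances and correlations, using all six scores also cuts the variance of change to 7/12 of the month-6 value, so the gain does not depend on dropout or on a transient pattern.

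The effect of early stopping is uncertain: about 0.14 points at the pilot's rate and at most about 0.9 at 5/32, both assuming a 6-point rise in stoppers. It is not established as a material bias for this regimen, and it is not the main reason to act. The Ki-67 sample size is unaffected.

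**What to change.** In 12.2, add a between-arm repeated-measures mixed model of the hot flash scores over months 1 to 6 in all randomized women, with terms for baseline score, arm, month and arm by month. Use every score obtained, including those after study agent is stopped, in keeping with the stated intent-to-treat principle. Report the arm difference averaged over months 1 to 6 together with the month-6 contrast. In 7.4, confirm that the Mayo score is what is recorded at the monthly calls. If an effect of early stopping is quoted, show the range from 1/42 to 5/32 and label it as an assumption.

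The cost is wording and a little more analysis, with no added visits or subjects if the schedule is followed as marked; if the calls do not now record the score, that item must be added to them. The averaged estimate gives less weight to an effect that appears only at month 6, which is why the month-6 contrast stays. The model assumes that missing scores are predictable from the observed ones, and scores collected after stopping reduce the reliance on that.

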13.0 REGULATORY

Any changes made to the protocol will be initiated by the Protocol Chair, and submitted to KUMC IRB (HSC) for approval. After KUMC IRB approval, other sites will submit revised protocol changes to local IRB for review.

The determination of the necessity to cease enrollment until revisions are approved will be determined by the Protocol Chair.

Novartis and NCI, DCP as the funder of the study, have the right to request discontinuation of the study at any time. A frequency of greater than grade 2 adverse events (exclusive of hot flashes and menstrual irregularities) that exceeds 20% will be cause for consideration of stopping the trial; unless there is adequate information to suggest that the adverse events are not related to the study agent.

